12.2.5	Exchange of Single Case Reports with Genentech.....	76
12.3	IND Annual Reports	78
12.4	Reporting to Regulatory Authorities, Ethics Committees and Investigators.....	78
12.5	AE/SAE Follow Up	78
13.	DATA AND SAFETY MONITORING PLAN (DSMP).....	80
14.	REFERENCES	82
	APPENDIX A: COCKCROFT-GAULT ESTIMATION OF CRCL.....	84
	APPENDIX B: INTERNATIONAL PROGNOSTIC INDEX (IPI) AND MIPI SCORES	85
	APPENDIX C: PERFORMANCE STATUS CRITERIA	86
	APPENDIX D: KNOWN STRONG IN VIVO INHIBITORS OR INDUCERS OF CYP3A	87
	APPENDIX E: DEAUVILLE CRITERIA FOR PET SCAN INTERPRETATION	88
	APPENDIX F: NEW YORK HEART ASSOCIATION (NYHA) CLASSIFICATION FOR CONGESTIVE HEART FAILURE	89
	APPENDIX G: FACT-LYM (VERSION 4)	90
	APPENDIX H: CORRELATIVE STUDIES LABORATORY INSTRUCTIONS	93
	APPENDIX I: RISKS OF FETAL EXPOSURE, PREGNANCY TESTING GUIDELINES AND ACCEPTABLE BIRTH CONTROL METHODS.....	94

PROTOCOL SUMMARY

Full Title:

A Multiple-center Phase 2 Study of Acalabrutinib-Lenalidomide-Rituximab (ALR) with an Expansion Cohort of Acalabrutinib-Lenalidomide-Obinutuzumab (ALO) in Patients with Previous Untreated Mantle Cell Lymphoma

Short Title:

Acalabrutinib-Lenalidomide-Rituximab (ALR) for Untreated Mantle Cell Lymphoma

Clinical Phase:

Phase II

Principal Investigator:

[name]., Ph.D.

Sample Size:

N=34

Accrual Ceiling:

The study will enroll up to 38 patients to account for screening failure and early drop out.

Study Population:*Inclusion criteria:*

- Histologically confirmed diagnosis of mantle cell lymphoma
- Age ≥ 18 years
- No prior systemic therapy for lymphoma
- Measurable disease defined by a tumor mass ≥ 1.5 cm in one dimension and measurable in two dimensions; patients with measurable spleen disease are allowed
- Treatment should be indicated according to the treating physician
- ECOG performance status ≤ 2
- Required initial laboratory parameters:
 - Absolute neutrophil count (ANC) ≥ 1000 cells/mm³
 - Platelet count $\geq 75,000$ cells/mm³
 - Calculated creatinine clearance ≥ 30 ml/min by Cockcroft-Gault formula

Total bilirubin \leq 1.5 x ULN

AST/SGOT and ALT/SGPT \leq 3.0 x ULN

- Able to take aspirin (81 or 325 mg) daily as prophylactic anticoagulation (patients intolerant to ASA may use low molecular weight heparin).
- All subjects must be registered into the mandatory Revlimid REMS® program, and be willing and able to comply with the requirements of Revlimid REMS®.
- Patients of reproductive potential agree to use highly effective birth control throughout their participation in this study, for at least 28 days following study termination, and for 160 days for males and 12 months for females after the last dose of rituximab, 180 days for males and 18 months for females after the last dose of obinutuzumab.
- Females of reproductive potential must adhere to the scheduled pregnancy testing as required in the Revlimid REMS® program. Females of childbearing potential (FCBP) must have a negative serum or urine pregnancy test with a sensitivity of at least 50 mIU/mL within 10 – 14 days and again within 24 hours prior to prescribing lenalidomide for Cycle 1 (prescriptions must be filled within 7 days). FCBP must either commit to continued abstinence from heterosexual intercourse or begin one highly effective method and one additional effective method AT THE SAME TIME, at least 28 days before and continue for at least 28 days after the last dose of lenalidomide (or 2 days after the last dose of acalabrutinib, whichever is longer). FCBP must also agree to ongoing pregnancy testing. Men must agree to use a latex condom during sexual activity with a FCBP through one week post last dose even if they have had a successful vasectomy. Men must also agree to refrain from sperm donation during the same timeframe. See Appendix: Risks of Fetal Exposure, Pregnancy Testing Guidelines and Highly Effective Birth Control Methods.
- Understand and voluntarily sign an ICF prior to any study related assessments and procedures are conducted.
- Able to adhere to the study visit schedule and other protocol requirements.

Exclusion criteria:

- Patients with blastoid histology
- Patients with known or suspected CNS involvement
- Viral infection with HIV or hepatitis type B or C. Seropositive HBV patients are eligible if they are negative for HBV DNA by PCR and receive concomitant antiviral therapy during treatment and for additional six months after coming off study.
- Prior history of malignancies other than MCL unless the patient has been disease free for \geq 5 years from the signing of the ICF. Exceptions include basal cell carcinoma or squamous cell carcinoma of the skin; carcinoma in situ of cervix; carcinoma in situ of breast, or localized prostate cancer

- Active uncontrolled systemic fungal, bacterial or viral infection (defined as ongoing signs/symptoms related to the infection without improvement despite appropriate antibiotics, antiviral therapy and/or other treatment)
- Clinically significant cardiovascular disease such as uncontrolled or symptomatic arrhythmias, congestive heart failure, or myocardial infarction within 6 months of screening, or any Class 3 or 4 cardiac disease as defined by the New York Heart Association Functional Classification.
- Malabsorption syndrome, disease significantly affecting gastrointestinal function, or resection of the stomach or small bowel that is likely to affect absorption, symptomatic inflammatory bowel disease, partial or complete bowel obstruction, or gastric restrictions and bariatric surgery, such as gastric bypass.
- Active bleeding or history of bleeding diathesis (e.g., hemophilia or von Willebrand disease).
- Uncontrolled AIHA (autoimmune hemolytic anemia) or ITP (idiopathic thrombocytopenic purpura).
- Requires treatment with a strong cytochrome P450 3A4 (CYP3A4) inhibitor/inducer. Patients on moderate CYP3A inhibitors can be considered for study after a washout period of at least 7 days.
- Requires or receiving anticoagulation with warfarin or equivalent vitamin K antagonists (e.g., phenprocoumon) within 7 days of first dose of study drug.
- Prothrombin time (PT)/INR or aPTT (in the absence of lupus anticoagulant) >2x ULN.
- Requires treatment with proton pump inhibitors (e.g., omeprazole, esomeprazole, lansoprazole, dexlansoprazole, rabeprazole, or pantoprazole). Subjects receiving proton pump inhibitors who switch to H2-receptor antagonists or antacids are eligible for enrollment to this study.
- History of significant cerebrovascular disease/event, including stroke or intracranial hemorrhage, within 6 months before the first dose of study drug.
- Major surgical procedure within 28 days of first dose of study drug. Note: If a subject had major surgery, they must have recovered adequately from any toxicity and/or complications from the intervention before the first dose of study drug.
- Patients with a history of toxic epidermal necrolysis or Stevens-Johnson syndrome
- Patients that are pregnant or breast feeding
- Known hypersensitivity to any study drug or excipients
- Patient on corticosteroids within two weeks prior to study entry, except for prednisone \leq 20 mg/day or equivalent for purposes other than treating MCL
- Use of any other experimental drug or therapy within 28 days of baseline
- Patient at high risk for deep vein thrombosis not willing to take DVT prophylaxis
- Any significant medical condition, laboratory abnormality, or psychiatric illness that would prevent the subject from participating in the study

- Known prior exposure to BTK inhibitor

Accrual Period:

07/2019 – 07/2022

Study Design:

This is a phase 2 study to evaluate the preliminary evidence of efficacy and safety of the combination of acalabrutinib, lenalidomide and rituximab (ALR), as well as acalabrutinib, lenalidomide and obinutuzumab (ALO), in previously untreated mantle cell lymphoma.

Study Duration:

Study includes an induction phase consisting of 12 cycles of ALR or ALO. Responding subjects will be eligible to enter a maintenance phase. Subjects will continue maintenance ALR or ALO, until disease progression, development of unacceptable toxicity, or voluntary withdrawal. Acalabrutinib and lenalidomide can be discontinued after 24 cycles of treatment (12 cycles of induction and 12 cycles of maintenance) for subjects achieving MRD-negative CR during maintenance phase. Subjects can be retreated with acalabrutinib and lenalidomide at time of disease progression.

Study Agent/ Intervention Description:

Cohort A: ALR in MCL, phase 2 study

- **Induction** (cycles 1 - 12)
 - 12 cycles, 1 cycle = 28 days
 - Acalabrutinib 100 mg BID continuous
 - Lenalidomide on days 1-21 (15 mg for cycle 1, then escalate as tolerated to 20 mg)
 - Rituximab 375 mg/m² on days 1, 8, 15, 21 of cycle 1 then day 1 of cycle 4, 6, 8, 10, 12
- **Maintenance** (cycle 13 – progression of disease or unacceptable toxicity)
 - Ongoing, 1 cycle = 28 days
 - Acalabrutinib 100 mg BID continuous
 - Lenalidomide 15 mg on days 1-21
 - Rituximab 375 mg/m² on day 1 of all even numbered cycles; e.g., 14, 16, 18, etc.

Cohort B: ALO in MCL, feasibility cohort

- **Induction** (cycles 1 - 12)
 - 12 cycles, 1 cycle = 28 days
 - Acalabrutinib 100 mg BID continuous
 - Lenalidomide on days 1-21 (15 mg for cycle 1, then escalate as tolerated to 20 mg)
 - Obinutuzumab on days 1, 8, 15 of cycle 1, day 1 of cycles 2-6, then every 2 cycles
- **Maintenance** (cycle 13 – progression of disease or unacceptable toxicity)

- Ongoing, 1 cycle = 28 days
- Acalabrutinib 100 mg BID continuous
- Lenalidomide 15 mg on days 1-21
- Obinutuzumab on day 1 of all even numbered cycles; e.g., 14, 16, 18, etc.

Primary Objective:

To determine the peripheral blood minimum residual disease (MRD)-negative complete response (CR) rate of the combination of ALR at the conclusion of 12 cycles of induction therapy.

Secondary Objectives:

- Safety and tolerability of the ALR combination
- Best overall response rate
- Complete response rate
- Progression free survival (time frame up to 2 years)
- Overall survival (time frame up to 2 years)
- Safety and feasibility of the ALO cohort

[figure not shown]
Exploratory Objectives:

- To evaluate peripheral blood MRD status during maintenance treatment.
- To estimate the response rate to the next subsequent therapy.
- To estimate the prevalence of adverse events over time.
- To estimate the quality of life of participants during the first 24 months of therapy.
- To correlate NGS mutational profile with response to treatment of the following genes: ATM, CCND1, TP53, KMT2D, NOTCH1, NOTCH2, WHSC1 and BIRC3.
- To evaluate the change in immune cells in peripheral blood, including T and NK cell subpopulations and the MDSC subset in response to treatment.
- To evaluate the cytokine profile (blood) in response to treatment.
- To analyze kinetics of changes of peripheral blood cell-free tumor DNA (cfDNA) in the plasma following study regimen and to evaluate cfDNA in the context of response status.
- To evaluate the immune metabolic profile (blood) pre-treatment, following ALR, and at time of progression.

Endpoints:

- The primary end point is to determine the peripheral blood MRD-negative CR rate (defined as MRD in peripheral blood $<10^{-6}$) of the ALR combination at the conclusion of 12 cycles of induction therapy.
- The secondary endpoints include progression-free survival (PFS), overall survival (OS), and time to next treatment of the ALR combination, as well as feasibility of ALO combination.

[figure not shown]
SCHEMA – ALR COHORT

Note

- Treatment includes 12 cycles of induction followed by maintenance. Patients will receive therapy until disease progression, development of unacceptable toxicity, or voluntary withdrawal. Acalabrutinib and lenalidomide can be discontinued after 24 cycles of treatment for subjects achieving MRD-negative CR during maintenance.
- MRD will be measured in peripheral blood at the conclusion of 6 and 12 cycles of induction treatment. Additional MRD measurements in peripheral blood will be collected every 4 cycles during maintenance.
- Imaging studies: PET/CT is required at baseline and time to confirm CR.

SCHEMA – ALO FEASIBILITY COHORT

Note

- Treatment includes 12 cycles of induction followed by maintenance. Patients will receive therapy until disease progression, development of unacceptable toxicity, or voluntary withdrawal. Acalabrutinib and lenalidomide can be discontinued after 24 cycles of treatment for subjects achieving MRD-negative CR during maintenance.
- MRD will be measured in peripheral blood at the conclusion of 6 and 12 cycles of induction treatment. Additional MRD measurements in peripheral blood will be collected every 4 cycles during maintenance.
- Imaging studies: PET/CT is required at baseline and time to confirm CR.

STUDY PROCEDURES – ALR

Table 1. Schedule of ALR Study Procedures¹

Procedure	Screening	Treatment Phase							Therapy Discontinuation	Follow-up Phase	
		Cycle 1				Subsequent cycles	Every 3 cycles Year 1	Every 4 cycles Year 2	Every 6 cycles Year 3-5		
		Day 1	Day 8±1	Day 15±1	Day 22±1						
Staging											
Lymph node/tissue biopsy ²	X										
Bone marrow aspirate & biopsy ³	X						Time to confirm CR				
Staging CT scan (or MRI) ⁴	X						X	X	X	X	
PET/CT ⁴	X						Time to confirm CR				
MRD Assay ⁵	X						Cycles 6 & 12	X	Every 6 cycles		
Laboratory Studies											
CBC with differential	X	X	X	X	X	X ¹²				X	
CMP including LFT	X	X	X	X	X	X				X	
LDH, uric acid ¹⁴ , phosphate ¹⁴ , PT/INR ¹⁴ , aPTT ¹⁴	X	X	X	X	X	X				X	
Creatinine clearance ⁶	X										
Thyroid function test TSH, T4, T3 uptake	X						X	X	X	X	
HBsAg, HBsAb, HBcAb, HCV, HIV ⁷	X										
HBV DNA testing ⁷	X						X	X	X	X	
Pregnancy testing ⁸	X	X				X				X	
Buccal Swab / saliva sample ²	X										
Other Evaluations											
Physical examination / vital signs ¹³	X	X	X	X	X	X				X	
Height & weight	X	X				X				X	
ECOG performance status	X	X				X				X	
MIPI score	X										
12-lead ECG ⁹	X										
FACT-Lym QOL questionnaires	X						X	X	X	X	
Concomitant medications	X	X	X	X	X	X				X	
Register Revlimid REMS® program	X										
Prescribe via Revlimid REMS® ¹⁰		X				X					
Adverse events assessment		X	X	X	X	X	X	X	X		
Correlative studies ¹¹		X	X	X	X	X				X	
Obtain Follow-Up treatment										X	

Obtain Follow-Up survival										X
---------------------------	--	--	--	--	--	--	--	--	--	---

¹ Unless otherwise specified, all screening requirements are within 28 days, all other assessments and procedures are +/- 3 days.

² LN/tissue biopsy has no time limit. Lymph node/tissue biopsy is required as necessary to confirm diagnosis. Additionally, one-time buccal swab or saliva sample collection for germline control should occur at screening, on treatment or off treatment.

³ During the study bone marrow biopsy is required only if the patient has otherwise fulfilled the criteria for CR. Baseline BMBx has no time limit.

⁴ Tumor assessment will be by means of PET/CT at Screening and at time to confirm CR. CT scan with contrast or MRI will be performed every 3 cycles year 1, every 4 cycles year 2, and every 6 cycles year 3 and beyond.

⁵ MRD assays are collected at baseline, after cycles 6 and 12 of induction, and then every 4 cycles year 2 during maintenance and then every 6 cycles afterwards (years 3-5).

⁶ Creatinine clearance (CrCl) is estimated using the Cockcroft-Gault formula where CrCl (mL/min) = $(140 - \text{age})(\text{weight [kg]}) / 72$ (serum creatinine [mg/dL]; for females, the formula is multiplied by 0.85 (Cockcroft, 1976). Creatinine clearance should be calculated using actual body weight.

⁷ All patients must be screened for hepatitis B and hepatitis C before starting treatment. Carriers of hepatitis B should be closely monitored, including HBV DNA testing at Screening, every 3 cycles year 1, every 4 cycles year 2, and every 6 cycles year 3 and beyond, and End of Treatment. For patients with evidence of prior HBV infection, HBV suppressive therapy is strongly recommended. HCV RNA viral load testing is suggested for patients with positive anti-HCV serology.

⁸ Pregnancy tests for females of childbearing potential. A female of childbearing potential (FCBP) is a sexually mature female who: 1) has not undergone a hysterectomy or bilateral oophorectomy; or 2) has not been naturally postmenopausal for at least 24 consecutive months (i.e., has had menses at any time in the preceding 24 consecutive months). Pregnancy test (serum or urine) is required at Screening, Day 1 of each cycle, and end of treatment.

⁹ 12-lead ECG is performed at screening/baseline, prior to maintenance, and as clinically indicated.

¹⁰ Lenalidomide must be prescribed through and in compliance with the Revlimid REMS® program of Celgene Corporation. Prescriptions must be filled within 7 days. Consideration should be given to prescribing lenalidomide 5 to 7 days in advance of Day 1 of each cycle to allow time for required patient and prescriber surveys, and drug shipment to patient. Any unused Revlimid® (lenalidomide) should be returned to the patient for disposition in accordance with the Revlimid REMS® program.

¹¹ Correlative study blood samples will be collected weekly for cycle 1, on C2D1, C4D1, and C6D1, then following the same frequency as the MRD collection and at time of progression.

¹² Consider weekly CBC for cycle 2 for subjects who have lenalidomide escalated from 15 mg to 20 mg.

¹³ Allow telemedicine / virtual visits after cycle 3 of induction during cycles when there is no infusion treatment, where physical exam, vital signs, height and weight may not be collected.

¹⁴ PT/INR/aPTT, as well as uric acid and phosphate assessments will be collected at baseline, and only if clinically indicated thereafter.

STUDY PROCEDURES – ALO

Table 2. Schedule of ALO Study Procedures¹

Procedure	Screening	Treatment Phase						Therapy Discontinuation	Follow-up Phase
		Cycle 1			Subsequent cycles	Every 3 cycles Year 1	Every 4 cycles Year 2		
		Day 1	Day 8±1	Day 15±1	Day 1±3				
Staging									
Lymph node/tissue biopsy ²	X								
Bone marrow aspirate & biopsy ³	X					Time to confirm CR			
Staging CT scan (or MRI) ⁴	X					X	X	X	X
PET/CT ⁴	X					Time to confirm CR			
MRD Assay ⁵	X					Cycles 6 & 12	X	Every 6cycles	
Laboratory Studies									
CBC with differential	X	X	X	X	X ¹²				X
CMP including LFT	X	X	X	X	X				X
LDH, uric acid ¹⁴ , phosphate ¹⁴ , PT/INR ¹⁴ , aPTT ¹⁴	X	X	X	X	X				X
Creatinine clearance ⁶	X								
Thyroid function test TSH, T4, T3 uptake	X					X	X	X	X
HBsAg, HBsAb, HBcAb, HCV, HIV ⁷	X								
HBV DNA testing ⁷	X					X	X	X	X
Pregnancy testing ⁸	X	X			X				X
Buccal Swab ²	X								
Other Evaluations									
Physical examination / vital signs ¹³	X	X	X	X	X				X
Height & weight	X	X			X				X
ECOG performance status	X	X			X				X
MIPI score	X								
12-lead ECG ⁹	X								
FACT-Lym QOL questionnaires	X					X	X	X	X
Concomitant medications	X	X	X	X	X				X
Register Revlimid REMS® program	X								
Prescribe via Revlimid REMS® ¹⁰		X			X				
Adverse events assessment		X	X	X	X	X	X	X	X
Correlative studies ¹¹		X	X	X	X				X
Obtain Follow-Up treatment									X

Obtain Follow-Up survival									X
---------------------------	--	--	--	--	--	--	--	--	---

¹ Unless otherwise specified, all screening requirements are within 28 days, all other assessments and procedures are +/- 3 days.

² LN/tissue biopsy has no time limit. Lymph node/tissue biopsy is required as necessary to confirm diagnosis. Additionally, one-time buccal swab collection for germline control should occur at screening, on treatment or off treatment.

³ During the study bone marrow biopsy is required only if the patient has otherwise fulfilled the criteria for CR. Baseline BMBx has no time limit.

⁴ Tumor assessment will be by means of PET/CT at Screening and at time to confirm CR. CT scan with contrast or MRI will be performed every 3 cycles year 1, every 4 cycles year 2, and every 6 cycles year 3 and beyond.

⁵ MRD assays are collected at baseline, after cycles 6 and 12 of induction, and then every 4 cycles year 2 during maintenance and then every 6 cycles afterwards (years 3-5)

⁶ Creatinine clearance (CrCl) is estimated using the Cockcroft-Gault formula where CrCl (mL/min) = $(140 - \text{age})(\text{weight [kg]}) / 72$ (serum creatinine [mg/dL]; for females, the formula is multiplied by 0.85 (Cockcroft, 1976). Creatinine clearance should be calculated using actual body weight.

⁷ All patients must be screened for hepatitis B and hepatitis C before starting treatment. Carriers of hepatitis B should be closely monitored, including HBV DNA testing at Screening, every 3 cycles year 1, every 4 cycles year 2, and every 6 cycles year 3 and beyond, and End of Treatment. For patients with evidence of prior HBV infection, HBV suppressive therapy is strongly recommended. HCV RNA viral load testing is suggested for patients with positive anti-HCV serology.

⁸ Pregnancy tests for females of childbearing potential (FCBP) is a sexually mature female who: 1) has not undergone a hysterectomy or bilateral oophorectomy; or 2) has not been naturally postmenopausal for at least 24 consecutive months (i.e., has had menses at any time in the preceding 24 consecutive months). Pregnancy test (serum or urine) is required at Screening, Day 1 of each cycle, and end of treatment.

⁹ 12-lead ECG is performed at screening/baseline, prior to maintenance and as clinically indicated.

¹⁰ Lenalidomide must be prescribed through and in compliance with the Revlimid REMS® program of Celgene Corporation. Prescriptions must be filled within 7 days. Consideration should be given to prescribing lenalidomide 5 to 7 days in advance of Day 1 of each cycle to allow time for required patient and prescriber surveys, and drug shipment to patient. Any unused Revlimid® (lenalidomide) should be returned to the patient for disposition in accordance with the Revlimid REMS® program.

¹¹ Correlative study blood samples will be collected weekly for cycle 1, on C2D1, C4D1, and C6D1, then following the same frequency as the MRD collection and at time of progression.

¹² Consider weekly CBC for cycle 2 for subjects who have lenalidomide escalated from 15 mg to 20 mg.

¹³ Allow telemedicine / virtual visits after cycle 3 of induction during cycles when there is no infusion treatment, where physical exam, vital signs, height and weight may not be collected.

¹⁴ PT/INR/aPTT, as well as uric acid and phosphate assessments will be collected at baseline, and only if clinically indicated thereafter.

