5. STUDY PROCEDURES

5.1 Study Design

This is a phase 2 study to evaluate the preliminary evidence of efficacy and safety of the combination of acalabrutinib, lenalidomide and rituximab (ALR), as well as the feasibility of acalabrutinib, lenalidomide and obinutuzumab (ALO), in previously untreated mantle cell lymphoma.

The study includes an induction phase consisting of 12 cycles of ALR or ALO. Responding subjects will be eligible to enter a maintenance phase. Subjects will continue maintenance ALR or ALO until disease progression, development of unacceptable toxicity, or voluntary withdrawal. Subjects in CR wishing to attempt stem cell collection following at least 6 months of induction treatment can hold lenalidomide for up to 30 days, and restart following stem cell collection.

Subjects will be monitored for MRD status in PB at baseline, and completion of 6 and 12 cycles of induction treatment using Adaptive Biotechnology Clonoseq assay, and then every 4 cycles. Acalabrutinib and lenalidomide can be discontinued after 24 cycles of treatment (12 cycles of induction and 12 cycles of maintenance) for subjects achieving MRD-negative CR for at least 4 months during maintenance phase, while rituximab or Obinutuzumab maintenance continues. Subjects can be retreated with adding back acalabrutinib and lenalidomide at time of disease progression.

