5.2.2 Treatment Phase

5.2.2.1 Cycle 1 Day 1, then Day 1 of all subsequent cycles

- Physical examination with vital signs and performance status
- AE assessment
- Concomitant medications
- CBC with differential
- Serum chemistries to include CMP, LDH, phosphate and uric acid
- Pregnancy test (for females of childbearing potential) (see appendix I)
- Correlative blood samples (Cycles 1, 2, 4, 6, 7, 13, 17, 21, 25, 29, 33 etc)
- Patients who discontinued oral medications and are on rituximab maintenance only, can have study visits on day 1 of cycles when treatment and laboratory studies are required.

5.2.2.2 Cycle 1, Days 8, 15, 22

- Physical examination with vital signs
- AE assessment
- Concomitant medications
- CBC with differential
- Serum chemistries to include CMP, LDH, phosphate and uric acid
- Correlative blood samples
- Subjects on ALO cohort can skip C1D22 visit

5.2.2.3 Cycles 4, 7, 10, 13, 17, 21, 25, then every 6 cycles onward

- Thyroid function test (TSH, T4, T3 uptake)
- HBV viral DNA in HBcAb positive, asymptomatic carrier
- CT scan (or MRI) of neck/chest/abdomen/pelvis (and other areas if indicated to evaluate sites of disease involvement); PET/CT to confirm CR

- Bone marrow aspirate and core biopsy (unilateral) only if otherwise in complete remission – not repeated once negative
- FACT-Lym quality-of-life questionnaires
- Correlative blood samples
- MRD assays at cycles 7 and 13, then every 4 cycles year 2 during maintenance, then every 6 cycles for years 3-5
- Telemedicine/virtual visits will be allowed after cycle 3 of induction during cycles when there is no infusion treatment, where physical exam and vital signs may not be collected.

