5.2.3 Treatment Discontinuation

At treatment discontinuation, subjects will undergo off study evaluations within 28 days of last dose.

- Physical examination with vital signs and performance status
- AE assessment
- CBC with differential
- Serum chemistries to include TFT, CMP, LDH, phosphate and uric acid
- Concomitant medications
- HBV viral DNA in HBcAb positive, asymptomatic carrier
- Correlative blood samples
- Pregnancy test (for females of childbearing potential)
- CT scan (or MRI) of neck/chest/abdomen/pelvis (and other areas if indicated to evaluate sites of disease involvement); PET scan at discretion of investigator
- FACT-Lym quality-of-life questionnaires
- Telemedicine/virtual visits will be allowed where physical exam and vital signs may not be collected.
- Follow-up contact every 6 months until death

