Implants and levonorgestrel-releasing intrauterine systems are associated with an increased risk of infection at the time of insertion and irregular vaginal bleeding. Prophylactic antibiotics should be considered particularly in patients with neutropenia.

Pregnancy testing

Medically supervised pregnancy tests with a minimum sensitivity of 50 mIU/mL must be performed for females of childbearing potential, including females of childbearing potential who commit to complete abstinence, as outlined below.

Before starting lenalidomide

Female Patients:

FCCP must have two negative pregnancy tests (sensitivity of at least 50 mIU/mL) prior to prescribing lenalidomide. The first pregnancy test must be performed within 10-14 days prior to prescribing lenalidomide and the second pregnancy test must be performed within 24 hours prior to prescribing lenalidomide. The patient may not receive lenalidomide until the Investigator has verified that the results of these pregnancy tests are negative.

Male Patients:

Must agree to practice complete abstinence or agree to use a condom during sexual contact with pregnant females or females of childbearing potential throughout the entire duration of lenalidomide treatment, during dose interruptions and for at least 28 days following lenalidomide discontinuation, even if he has undergone a successful vasectomy.

During study participation and for 28 days following lenalidomide discontinuation

Female Patients:

- FCBP with regular or no menstrual cycles must agree to have pregnancy tests weekly for the first 28 days of lenalidomide treatment, including dose interruptions and then every 28 days throughout the remaining duration of lenalidomide treatment, including dose interruptions, at lenalidomide discontinuation, and at Day 28 following lenalidomide discontinuation. If menstrual cycles are irregular, the pregnancy testing must occur weekly for the first 28 days of lenalidomide treatment, including dose interruptions, and then every 14 days throughout the remaining duration of lenalidomide treatment, including dose interruptions, at lenalidomide discontinuation, and at Day 14 and Day 28 following lenalidomide discontinuation.
- At each visit, the Investigator must confirm with the FCBP that she is continuing to use two reliable methods of birth control at each visit during the time that birth control is required.

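### The visit tables and visit lists omit pregnancy tests that Appendix I makes mandatory during and after lenalidomide

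*Combined protocol and SAP*

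**What the plan says.** Footnote 8, identical on this point in Table 1 (ALR) and Table 2 (ALO), says: "Pregnancy test (serum or urine) is required at Screening, Day 1 of each cycle, and end of treatment". The table rows agree with it: the pregnancy-test row is blank on Cycle 1 Days 8 and 15 in both tables and on Day 22 in Table 1. Table 2 has no Day 22 column.

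The visit lists follow the tables.

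- Section 5.2.2.1 (Day 1 visits) carries the entry "Pregnancy test (for females of childbearing potential) (see appendix I", with its pointer to the appendix.
- Section 5.2.2.2 (Cycle 1 Days 8, 15 and 22) lists no pregnancy test and no pointer. It adds: "Subjects on ALO cohort can skip C1D22 visit".
- Section 5.2.3 lists one pregnancy test at treatment discontinuation, when "subjects will undergo off study evaluations within 28 days of last dose".

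Appendix I sets a fuller schedule. All FCBP must have "pregnancy tests weekly for the first 28 days of lenalidomide treatment". After that, testing is every 28 days if menses are regular or absent. If they are irregular it is "every 14 days throughout the remaining duration of lenalidomide treatment". When lenalidomide stops, women with regular or no menses are tested at discontinuation and at Day 28 after it. Those with irregular menses are tested "at lenalidomide discontinuation, and at Day 14 and Day 28 following lenalidomide discontinuation".

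Section 5.1 allows both oral drugs to stop after 24 cycles in patients with MRD-negative CR, "while rituximab or Obinutuzumab maintenance continues".

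**The concern.** Section 5.2 sends the reader to Tables 1 and 2 for every scheduled visit and assessment, so site staff will reasonably treat those tables as complete. Yet they omit tests that Appendix I makes mandatory. Blood counts and chemistry are marked on the same cycle 1 days, so the blank pregnancy cells read as intended rather than overlooked.

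The stake is participant safety. Appendix I says that a teratogenic effect in humans cannot be excluded and requires a pregnancy risk minimisation plan. A site working exactly to the tables would depart from that plan in cycle 1 for every FCBP, and at more time points for those with irregular menses.

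**Working it through.** The plan gives no figure to reproduce, so the check is a count of scheduled tests under each text.

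**Assumptions.** Cycles last 28 days with no delays, lenalidomide starts on Cycle 1 Day 1, and the first weekly test is the Day 1 test. Screening and pre-prescription tests are left out of the counts.

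**Inputs.** Tables: one test per cycle, on Day 1 (footnote 8). Appendix I: weekly for 28 days, then every 28 or every 14 days. Visit window: plus or minus 3 days (footnote 1). Lenalidomide is taken on Days 1 to 21 (Section 5.1.2).

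**On treatment**

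| Period | Tables | Appendix I, regular or no menses | Appendix I, irregular menses |
|---|---|---|---|
| Cycle 1 | 1 | 28/7 = 4 (Days 1, 8, 15, 22) | 4 |
| Each later cycle | 1 | 28/28 = 1 | 28/14 = 2 |
| 12 induction cycles | 12 | 4 + 11 × 1 = 15 | 4 + 11 × 2 = 26 |
| 24 cycles | 24 | 4 + 23 × 1 = 27 | 4 + 23 × 2 = 50 |

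Over 24 cycles the shortfall is 27 − 24 = 3 tests (regular or no menses), all of them in cycle 1, or 50 − 24 = 26 (irregular menses). For regular or no menses the two schedules agree from cycle 2 until discontinuation.

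**After lenalidomide, all treatment stopping together.** Section 5.2.3 gives 1 test, on any day up to 28 days after the last dose. Appendix I requires 2 (discontinuation and Day 28), or 3 with Day 14 if menses are irregular. One test cannot serve two dates.

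**After lenalidomide, antibody continuing.** Suppose the last dose is on Cycle 24 Day 21. The end-of-treatment test is not triggered, because treatment has not ended. The next tests in the tables are:

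- Cycle 25 Day 1: 28 − 21 + 1 = 8 days after the last dose, or 5 to 11 days with the window.
- Cycle 26 Day 1: 8 + 28 = 36 days after the last dose, or 33 to 39 days with the window.

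Neither range contains Day 14 or Day 28. If discontinuation is dated instead from Cycle 25 Day 1, that visit supplies the test at discontinuation and Cycle 26 Day 1 falls on Day 28. Nothing falls on Day 14.

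**Tests with no scheduled visit.** ALO Cycle 1 Day 22; the mid-cycle tests for irregular menses in either cohort; the Day 14 test after lenalidomide; and the Day 28 test when counted from the last dose.

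**The case against.** The best reply is that this is an omission and not a clash of rules. Footnote 8 does not say that its list is exhaustive, and a site that follows Appendix I also satisfies the tables. The stricter duty is signposted in several places: inclusion criteria in Section 3.2 make REMS pregnancy testing a condition of entry and name Appendix I, Section 5.2.2.1 points to it, and footnote 10 of both tables requires prescribing in line with REMS.

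Part of this stands. The stricter rule is already in the protocol, and the signposts show which schedule is intended. They do not put a test on Days 8, 15 or 22. The only pointer within the visit lists is in the Day 1 list, not where the cycle 1 tests are missing. The documents do not reproduce the REMS schedule, so the comparison here rests on Appendix I alone.

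Three limits on size also stand. The 24-against-50 count applies only to irregular menses. The single test after lenalidomide applies only when all treatment stops together. With the antibody continuing, and discontinuation dated from Cycle 25 Day 1, women with regular or no menses have no gap after lenalidomide.

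**Conclusion.** The inconsistency is real and should be corrected. Footnote 8 of both tables, Section 5.2.2.2 and Section 5.2.3 leave out tests that Appendix I requires.

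The firmest part is cycle 1: three missing tests for every FCBP in either cohort, whatever their menstrual pattern. The 14-day and Day 14 gaps concern only those with irregular menses. The Day 28 gap when the antibody continues depends on how lenalidomide discontinuation is dated, which Appendix I does not define.

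No endpoint, analysis or stopping rule is affected. The number of FCBP is not given. Enrolment is at most 38 (Section 11.2) and Section 2.3 gives a median age of 65 for MCL, so few women are likely to be involved.

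**What to change.** - **Table 1:** mark a pregnancy test on Cycle 1 Days 8, 15 and 22.
- **Table 2:** mark Days 8 and 15 and add a Day 22 test, done at a local laboratory if that visit is skipped.
- **Section 5.2.2.2:** add the test to the list.
- **Footnote 8 of both tables:** cite and follow Appendix I, including 14-day testing after the first 28 days for irregular menses. Citing it also brings in the two pre-prescription tests (10 to 14 days before, and within 24 hours), which the footnote now reduces to Screening and Day 1.
- **Section 5.2.3 and footnote 8:** tie the later tests to lenalidomide discontinuation, not only to the end of all treatment. Require them at discontinuation and at Day 28, plus Day 14 if menses are irregular. State the date from which those days are counted.

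A cross-reference alone in footnote 8 and Sections 5.2.2.2 and 5.2.3 would settle the wording, but the blank cells that staff work from would remain.

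The cost is table marks and text edits. Visits with blood draws already exist on ALR Days 8, 15 and 22 and ALO Days 8 and 15. ALO Day 22, the mid-cycle tests and the tests at Day 14 and Day 28 after lenalidomide need a few local-laboratory tests. Appendix I already requires all of them, so no new requirement is created.
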